Subjects will be followed until the last subject enrolled has completed the 1 year follow-up visit or until PMA approval is obtained in the US (whatever is later), however, Medtronic will work with FDA to determine if longer term follow after PMA approval is required. A post-approval analysis of 1-year Major Device Event (MDE) rate is planned.

6. Determination of Sample Size

One hundred (100) enrolled subjects will ensure 87 evaluable subjects at 30 days. The primary endpoint analysis will be completed upon 87 evaluable subjects reaching the 30 day endpoint. Based on Valor II study results, Valiant Evo is expected to perform similarly and have 6% of MDE combined with access and/or deployment failures at 30 days. The sample size of 87 evaluable subjects will provide 85% statistical power for the study hypothesis. The type I error is controlled at the one-sided 0.025 level.

Table 1: Power Analysis

True rate of MDEs combined with access and/or deployment failures at 30 day with Valiant Evo	6%
Performance Goal	16%
Significance level	0.025
Statistical test	One-sided binomial test
Evaluable sample size	n=87
Enrollment	Minimum of 100 subjects enrolled to ensure 87 evaluable subjects
Statistical power from the 87 evaluable subjects	85%

One hundred (100) enrolled subjects will also ensure 63 evaluable subjects at 1-year on MDE rate for the post-approval analysis. The VALOR II study with the Valiant stent graft system enrolled 160 patients with DTAA and was assessed through 12 months for purposes of PMA (P100040) approval. Through 1-year post-

treatment, the rate of MDEs combined with access and/or deployment failures was 7.1% (11/153) (Medtronic internal data using the Valiant Evo proposed definition). Therefore, for the purpose of post approval analysis, the rate of MDEs combined with access and deployment failures at 1-year with Valiant Evo is estimated to be 7.1% (refer to Table 22 below for power analysis assumptions).

Table 2: Power Analysis for Post-approval Analysis of 1-year Endpoint

Estimated rate of MDEs combined with access and/or deployment failures at 1 year with Valiant Evo	7.1%
Performance Goal (PG) at 1-year	20%
Significance level	0.05
Statistical test	One-sided binomial test
Evaluable sample size	N = 63 at 1 year
Enrollment	IDE cohort will enroll a minimum of 100 subjects and is expected to have a minimum of 63 evaluable subjects at 1-year follow up.

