Statistical power from 63 or more evaluable subjects	92% (overall study power for passing both hypotheses is 81%)

7. Statistical Methods

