7.9. Evaluation of Objectives

Primary Endpoint

The primary objective will be assessed by the composite safety and effectiveness endpoint that is based on the proportion of subjects who experienced:

- (a) Access and/or deployment failures; and/or
- (b) Major device effects (MDE) within 30 days post index procedure

MDEs include the occurrence of any of the following:

- Device-related secondary procedures
- Device-related mortality
- Conversion to open surgery
- Thoracic aortic aneurysm rupture

Detailed definitions of MDEs are defined in Clinical Investigational Plan Appendix L.5.

The primary study endpoint will be tested against a performance goal of 16% at 30 days:

$$H_0: p \geq 16\% \text{ vs. } H_a: p < 16\%,$$

where p denotes the true event rate of primary study endpoint in the target population. If the null hypothesis

(H₀) is rejected at the one-sided 0.025 statistical significance level, it is considered that the performance goal for the primary endpoint has been reached.

The analysis set of all enrolled subjects will be used for the analysis. The primary study endpoint is a dichotomous study outcome; hence, an exact method based on the binomial distribution will be used for the hypothesis testing.

Primary Endpoint Calculation:

A subject will be a failure on the primary endpoint if the subject either failed on access/deployment or had an MDE within 30 days. A subject will be a success on the primary endpoint if the subject is confirmed for access and deployment success as well as free from MDE. The failure rate of the primary endpoint is the percent of failures in all the evaluable subjects for the endpoint, i.e., in total number of failures and successes. Note that a subject who had an MDE within 30 days is one of the subjects in m as defined below. A subject who is free from MDE is one of the subjects in k as defined below.

MDE Rate Calculation:

All MDEs will be adjudicated by the Clinical Event Committee (CEC) per study protocol. MDE rate will be calculated as follows (Table 5):

Table 5: MDE Rate Calculation:

MDE rate = $m/(m + k)$	Within 30 Days	Within 183 Days	Within 365 Days
m = No. of Subjects Who Had MDE(s)	No. of subjects who had at least one MDE with onset day from Day 0 to Day 30, inclusive.	No. of subjects who had at least one MDE with onset day from Day 0 to Day 183, inclusive.	No. of subjects who had at least one MDE with onset day from Day 0 to Day 365, inclusive.

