k = No. of Subjects Who Had No MDE	No. of subjects who have been in study for at least 1 day and without an MDE.	No. of subjects who have been in study for at least 91 days and without an MDE.	No. of subjects who have been in study for at least 305 days and without an MDE.

If a subject is early terminated from the study, the last day that the subject has been seen will be the duration in study, which can be the day of last follow-up, last imaging taken, an AE reported, or withdrawal from the study. If a subject is still in the study, the duration in study will be the time from index procedure to the cut off day that the database is locked or data snapshot is taken.

Subgroup analyses by-sex, by-race (based on subjects enrolled in the US only, since collection of race and ethnicity data may not be allowed outside the US as per local law and regulation), FreeFlo versus Closed Web configuration as proximal component, percutaneous access versus non-percutaneous, and by-region/study site will be performed on the primary study endpoint using descriptive statistics and reviewed for

clinical significant difference.

Secondary Endpoints

30-day Secondary Endpoint

The following secondary endpoints will be evaluated within 30 days post treatment:

- Peri-operative mortality
- All adverse events (AE) within 30 days including:
 - Major Adverse Event(s) (MAE)
 - Serious Adverse Event(s) (SAE)
- Secondary procedures
- Loss of stent graft patency at 30 day visit based on imaging findings
- Endoleaks at 30 day visit based on imaging findings

Detailed definitions of MAEs are defined in the Clinical Investigational Plan Appendix L.2.2. MAEs will be identified using codes in the Medical Dictionary for Regulatory Activities (MedDRA) provided by the Medtronic Clinical Safety group.

6-month Secondary Endpoints:

The following secondary endpoints will be evaluated:

- All-cause mortality within 183 days
- Aneurysm-Related Mortality within 183 days
- MDEs within 183 days
- All AEs within 183 days including:
 - MAEs
 - SAEs
- Secondary procedures within 183 days
- Loss of stent graft patency within 6 months based on imaging findings
- Endoleaks at 6 months based on imaging findings

- Stent graft migration at 6 months as compared to 1-month imaging
- Aneurysm expansion > 5mm at 6 months based on imaging findings relative to the 1-month visit

12-month Secondary Endpoints

The following secondary endpoints will be evaluated:

- All-cause mortality within 365 days

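### If the 1-year test uses Table 5's 365-day rule, Table 2's 92% power does not hold at the stated minimum of 63 evaluable of 100 enrolled; at exactly 63 it is about 60% to 82%, depending on when subjects leave (minor)

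*SAP*

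**What the plan says.** SAP section 6, Table 2 plans a one-sided binomial test at the 0.05 level. The assumed 1-year rate of MDE plus access or deployment failure is 7.1%, and the goal is 20%. The cohort of at least 100 enrolled "is expected to have a minimum of 63 evaluable subjects at 1-year follow up". The power row, labelled "Statistical power from 63 or more evaluable subjects", reads "92% (overall study power for passing both hypotheses is 81" per cent.

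SAP 7.9, Table 5 defines the 365-day MDE rate as m/(m+k):

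- m is "No. of subjects who had at least one MDE with onset day from Day 0 to Day 365, inclusive", with no minimum follow-up.
- k is "No. of subjects who have been in study for at least 305 days and without an MDE".

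The same section defines the 30-day failure rate as "the percent of failures in all the evaluable subjects for the endpoint, i.e., in total number of failures and successes", and ties those failures and successes to m and k. For 30 days, k asks only for "No. of subjects who have been in study for at least 1 day and without an MDE".

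On time in study, SAP 7.9 adds: "If a subject is still in the study, the duration in study will be the time from index procedure to the cut off day" of the data. A missed visit alone therefore removes nobody from k.

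The SAP does not write out the 1-year test. Table 5 is written for MDE alone, while Table 2 tests the composite. SAP section 3 refers questions of clarification to the US trial protocol, which is not among the documents.

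**The concern.** The two halves of the Table 5 fraction treat drop-outs differently. A subject who has an event and then leaves stays in m. A subject who leaves event-free before Day 305 is in neither m nor k. If leaving is unrelated to outcome, the rate is pushed upward. The push is strong here because, on the SAP's figures, most 1-year events occur by Day 30, so someone who leaves later has already passed most of the risk.

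Table 2 allows up to 37 of 100 subjects to be non-evaluable, yet computes power as if the other 63 still carried the unselected 7.1% rate. A device performing exactly as assumed could therefore miss the 20% goal more often than the plan says. The stated 81% joint power is exposed too, since joint power cannot exceed the power of either test. The descriptive non-imaging rates through 1 year use the same rule (SAP 7.9) and share the upward bias.

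**Working it through.** **Inputs from the SAP (section 6 and 7.9).** 100 enrolled; 6% events by Day 30; 7.1% by Day 365; goal 20%; one-sided 0.05; minimum 63 evaluable; 305-day rule for k.

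**Assumptions.** Drop-out is independent of outcome. Its timing is not stated, so it is varied. Events are uniform over Days 0–30 (6 points) and Days 30–365 (1.1 points).

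**1. Reproduce Table 2.** Exact binomial with n = 63 and goal 20%: P(X ≤ 7) = 0.047 and P(X ≤ 8) = 0.094, so the test passes with 7 or fewer events. At 7.1%, P(X ≤ 7) = 0.923, which is the stated 92%. The expected count is 63 × 0.071 = 4.5 events. Table 1 also reproduces: n = 87, goal 16%, pass with 7 or fewer, power 0.849 (stated 85%).

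**2. Expected rate under Table 5.** Let d be the share lost before Day 305 and q the chance that a lost subject had an event before leaving. Per enrolled subject:

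- m = (1 − d) × 0.071 + d × q
- k = (1 − d) × 0.929
- rate = m/(m + k), with d chosen so that 100 × (m + k) is about 63

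*All loss just before Day 305:* q = 0.060 + 0.011 × 274.5/335 = 0.0690 and d = 0.397. Then m = 0.0428 + 0.0274 = 0.0702, k = 0.603 × 0.929 = 0.5602, and the rate is 0.0702/0.6304 = 11.1%. With 63 evaluable, P(X ≤ 7) = 0.596.

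*All loss spread over month 1:* q = 0.030 (half of 6%) and d = 0.381. Then m = 0.0439 + 0.0114 = 0.0554, k = 0.5751, and the rate is 8.8%. P(X ≤ 7) = 0.814.

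*All loss on Day 0:* q = 0, the rate stays 7.1%, and power is 0.923.

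**3. Simulation check** (200,000 trials of 100 subjects, exact test at the realised m + k, loss tuned so that m + k averages 63):

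| Loss pattern | Mean m | Mean rate | Power at exactly 63 | Power averaged |
|---|---|---|---|---|
| All just before Day 305 | 7.0 | 11.1% | 60% | 53% |
| Exponential | 6.7 | 10.6% | 65% | 59% |
| 13% on Day 0, then exponential | 5.9 | 9.4% | 76% | 70–71% |
| All in month 1 | 5.5 | 8.8% | 82% | 76% |
| All on Day 0 (no bias) | 4.5 | 7.1% | 92% | 89% |

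About 45% of the averaged trials fall below 63. The exact-63 column is therefore the like-for-like comparison with Table 2.

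**4. How much loss the 92% tolerates** (averaged power):

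| Loss before Day 305 | Late | Exponential | All in month 1 | 13% on Day 0, then exponential |
|---|---|---|---|---|
| 4% | 97% | 97% | 98% | – |
| 15% | 92% | 92% | 95% | 96% |
| 20% | 87% | 88% | 92% | 93% |
| 22% | 85% | 86% | 91% | 92% |

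**5. Joint power.** At exactly 63 the 1-year power caps joint power at 60%, 65% or 76% in the first three patterns, all below 81%. The month-1 cap (82%) does not by itself rule out 81%. Away from the floor, under exponential loss, joint power is 83% at 20% loss and 80% at 25%.

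**The case against.** **63 is a floor, not a forecast.** This stands. The only attrition evidence in the documents is the earlier study's 153 of 160 in the 1-year denominator, so 7/160 = 4.4% were not counted. At about that loss, power is 97%, above the stated 92%. Nothing suggests that 37% loss is expected. Still, Table 2 prints 92% for 63 or more, so the figure should hold at 63.

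**A reader might take 53% to 76% as the power at the floor, or 15% as the limit of tolerable loss.** The documents support neither as a general statement. The 53–76% range averages over trials, many of them below the stated minimum. The 15% limit belongs to exponential or late loss; with early loss it is about 20% to 22%.

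**Loss could all fall on Day 0, leaving no bias.** Arithmetically true. But the 30-day k needs only one day in study, so losing 37 on Day 0 would leave about 63 evaluable at 30 days, against the 87 that SAP section 6 expects.

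**The SAP never says that the 1-year test uses Table 5.** This stands as a caveat. The inference rests on its being the only 365-day rule and on the 30-day definition of evaluable. The US protocol might say otherwise. Access and deployment failures occur at the procedure and would also be retained, so including them does not reverse the direction.

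**A reader might infer a threat to the approval decision.** The documents do not support that. The bias works against the device and creates no false-success risk. The 30-day primary test is unaffected, and SAP 7.5 makes the 1-year analysis conditional on PMA approval.

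**Other provisions might cover it.** They do not. SAP 7.4 imputes no outcomes, and its optional tipping-point analysis concerns the primary endpoint. Kaplan-Meier event rates begin beyond 1 year, except for all-cause and aneurysm-related mortality (SAP 7.10).

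**Conclusion.** The point holds in a limited form and is minor. If Table 5 governs the 1-year test, Table 2's 92% does not follow from the stated rule at the stated minimum: with exactly 63 evaluable, power is about 60% to 82% under the post-procedure loss patterns examined. The 81% joint figure fails there under most of them. With low attrition, such as the earlier study's, the stated figures are met or exceeded. The arithmetic is firm. The size depends on assumed drop-out timing and on drop-out being unrelated to outcome, and the premise rests on an inference that the US protocol could settle. The evidence earns a corrected power statement. It does not show that the exact test must be replaced: a large-sample limit resting on about 7 events would be a debatable substitute.

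**What to change.** 1. In SAP section 6, Table 2, restate the 1-year and joint power under the Table 5 rule as a range, with the assumed level and timing of attrition shown.
2. In SAP 7.9, state that the 1-year composite test uses the Table 5 rule, if that is intended, and how access and deployment failures enter m and k.

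Optional: report a Day-365 Kaplan-Meier or cumulative-incidence estimate in all enrolled subjects as a sensitivity analysis beside the exact test, and show the number excluded from k with each descriptive 1-year rate.

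The cost is one recomputed table and a few sentences. No new patients or data are needed, and the two required changes alter no planned analysis.

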### F.2.4 Follow-Up Visits and Procedures

Each subject will have required post-implantation follow-up visits at 30 days and 12 months. Follow-up visits and associated timeframe windows are summarized in Table F-1.

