**Table F-1: Post-Implantation Follow-Up Visit Schedule and Windows**

Follow-Up Visit	Window Start Day	Target Day	Window Close Day
1 Month (± 15 days)	15	30	45
12 Months (365 ±60 days)	305	365	425

At all required follow-up visits subjects will undergo the following assessments and procedures:

- Physical Examination
- Chest CT/MRI with contrast
- EQ-5D questionnaire
- Adverse event assessment

A CT/MRI with contrast acquired at discharge (or before day 15) due to medical necessity may be used to meet the 1-month follow-up visit CT/MRI requirement if a CT/MRI with contrast cannot be obtained within the 1-month follow-up window due to the subject's health status based upon physician discretion. If conversion to open repair is required during the follow-up period, then the subject will return for the 30-day follow-up visit, if applicable. Thereafter the subject will be followed per institutional standard of care and serious adverse events will be recorded in the eCRF until the total duration of the trial. At the end of the study the exit form should be completed.

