#### *F.7.4 Lost-to-follow-up*

A subject may be considered lost to follow-up once there are 3 documented attempts by the investigator and/or research staff to contact the subject. The third attempt should be made by mail to the subject and phone call or mail to the subject's emergency contact.

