At enrollment, those subjects who sign and date the informed consent document, meet all of the study eligibility criteria, and are approved by the IPR will be eligible for inclusion into the Valiant Evo US Clinical Trial. The subject will only be considered enrolled when arterial access is established and an attempt to introduce the Valiant Evo Thoracic Stent Graft is made. A single, primary stent graft may be used by itself if its size is sufficient to provide the desired coverage. Alternatively, it may be used in combination with additional stent graft sections that increases the graft length distally or proximally to the primary section.

The Valiant Evo Global Clinical program will be conducted under both the Valiant Evo US Clinical Trial protocol and Valiant Evo International Clinical Trial protocol, and will enroll up to 37 sites worldwide. Inclusion will be halted at sites that reach the 20% inclusion cap. There will be no minimum number of subjects for a single investigational site. Globally, a total of 100 subjects will be concurrently enrolled in the United States and outside the United States to support the primary endpoints. Up to 50% of subject data used to support PMA approval may come from subjects enrolled at sites outside of the US under the Valiant Evo International Clinical Trial protocol.

The primary endpoint analysis will be completed upon 87 evaluable subjects reaching the 30 day endpoint. The data obtained from these 87 evaluable subjects will be used to support PMA-s Approval of the Valiant Evo Thoracic Stent Graft System and to support any other future Medtronic submissions to regulatory bodies.

Subjects enrolled under the Valiant Evo US Clinical Trial require follow-up evaluations at the following time points:

- 1 month following the index procedure (30 ± 15 days)
- 6 months following the index procedure (183 ± 30 days)
- 12 months following the index procedure (365 ±60 days)
- 24 months following the index procedure (730 ±60 days)
- 36 months following the index procedure (1095 ±60 days)

- 48 months following the index procedure (1460 ±60 days)
- 60 months following the index procedure (1825 ±60 days)

Note that the 6-month follow up is not mandatory for subjects enrolled under the Valiant Evo International Clinical Trial protocol. Available 6-month follow-up data from the international trial will be used for analysis.

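### Subjects not formally exited are credited with follow-up to the data cut-off, so unobserved time can count as event-free in the 183- and 365-day non-image rates

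*SAP*

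**What the plan says.** SAP 7.9 defines the MDE rate as m/(m + k), where m counts subjects with an MDE and k counts subjects without one. Entry to k depends on time in study. For the 183-day rate Table 5 requires "No. of subjects who have been in study for at least 91 days and without an MDE"; for the 365-day rate it requires "No. of subjects who have been in study for at least 305 days and without an MDE".

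Time in study is then defined in two ways:

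- Early termination: "If a subject is early terminated from the study, the last day that the subject has been seen will be the duration in study".
- Everyone else: "If a subject is still in the study, the duration in study will be the time from index procedure to the cut off day", meaning the date of database lock or data snapshot.

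The same section says that mortality, secondary procedures, MAEs, SAEs, conversion and rupture through 1 year are calculated in the same way.

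The pooled data include subjects from the International protocol. Its section F.2.4 states "Each subject will have required post-implantation follow-up visits at 30 days and 12 months", with windows of Day 15 to 45 and Day 305 to 425 (Table F-1). SAP section 5 adds: "Note that the 6-month follow up is not mandatory for subjects enrolled under the Valiant Evo International Clinical Trial protocol". Loss to follow-up is a discretionary label in Protocol F.7.4: "A subject may be considered lost to follow-up once there are 3 documented attempts". A missed visit is recorded with its reason (F.7.3) but is not listed in F.7.1 as a reason for exit.

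**The concern.** Two subjects with the same last contact, say Day 30, are treated differently according to paperwork. The one who formally withdraws leaves the denominator of the 183- and 365-day rates. The one who simply has not been seen again stays in and is scored as a success. Time in which nobody checked on the subject is counted as time without an event.

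An event that has not been ascertained cannot enter m, while the subject still enters k, so the error can only lower the rate. It falls on the 6- and 12-month safety and effectiveness rates that support the PMA. It matters most at snapshots taken before the 12-month visits are complete, because the International schedule has a built-in gap of 260 days (305 − 45) without a required visit.

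**Working it through.** **1. The plan's own 1-year figure.** SAP section 6, Table 2: n = 63, goal 20%, true rate 7.1%, one-sided 0.05, exact binomial. The largest passing count is 7, since P(X ≤ 7 | 63, 0.20) = 0.0473. Power = P(X ≤ 7 | 63, 0.071) = 92.3%, against the stated 92%. The power figure reproduces. The question is who is entitled to be counted among the evaluable subjects.

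**2. One subject traced through the rules.** Take an International subject seen on Day 30, with no MDE recorded, no later contact and no exit form.

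| Cut-off (days after procedure) | Last day seen | Duration under SAP 7.9 | In k at 183 days (≥ 91)? | In k at 365 days (≥ 305)? |
|---|---|---|---|---|
| 90 | 30 | 90 | no | no |
| 91 | 30 | 91 | yes | no |
| 305 | 30 | 305 | yes | yes |
| any, but formally exited | 30 | 30 | no | no |

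**3. How many subjects could be in these day ranges at a snapshot.** This needs an accrual pattern, which the documents do not settle. Protocol C.8 expects inclusion within 12 months; L.3.3.4 expects about 30 months. Assume even accrual of 47 subjects and a snapshot at which the day range is fully populated. Expected number = 47 × (days in range) / (accrual days).

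| Range at snapshot | 30 months (913 days) | 12 months (365 days) |
|---|---|---|
| Day 91–304 (214 days) | 47 × 214/913 = 11.0 | 47 × 214/365 = 27.6 |
| Day 305–364 (60 days) | 47 × 60/913 = 3.1 | 47 × 60/365 = 7.7 |
| Day 305–425 (121 days) | 47 × 121/913 = 6.2 | 47 × 121/365 = 15.6 |

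The first row holds subjects credited at 183 days with no required visit since month 1. The other two hold subjects credited at 365 days whose 12-month visit may or may not have taken place. All are ceilings on the number unseen at such a snapshot. At a cut-off after every 12-month window has closed, the pending group is empty and only subjects who missed the visit and have not exited remain.

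**4. Effect on the reported rate.** Let u be the number unseen and event-free on record. The rule as written gives m/N; leaving those subjects out gives m/(N − u). With N = 100 and assumed u:

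- 365 days, m = 7: 7/100 = 7.0% as written; 7/95 = 7.4% (u = 5), 7/90 = 7.8% (u = 10), 7/80 = 8.8% (u = 20).
- 183 days, m = 6: 6/100 = 6.0% as written; 6/90 = 6.7% (u = 10), 6/78 = 7.7% (u = 22).

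The second figure in each comparison is itself high if the snapshot is immature, because early events stay in m while event-free subjects drop out.

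**5. The 1-year test, if Table 5 feeds it.** With 100 counted, the largest passing count is 13 (exact level 0.0469). Suppose the true 1-year rate is 20% and unseen subjects show only their 30-day events, at an assumed 16%. The type I error is P(Bin(100 − u, 0.20) + Bin(u, 0.16) ≤ 13): 0.052 for u = 5, 0.057 for u = 10, 0.069 for u = 20.

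**The case against.** The strongest reply is that the gap is smaller than the visit schedule suggests. Adverse events are collected throughout (Protocol F.6.2), and SAEs are due within 3 days of the site learning of them (Table F-4). A missed visit must be documented and is a listed deviation (F.7.3, F.8). The investigator must tell the sponsor when a subject cannot be followed (F.7.2). A completed 12-month visit includes an adverse event assessment, and events are dated by onset, so it fills the earlier gap retrospectively. Mortality is also reported by Kaplan-Meier (SAP 7.10), and the secondary endpoints are descriptive. All of this stands and reduces the size. None of it forces a formal exit or makes contact a condition for entering k, so the direction is unchanged.

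SAP section 5 also says that available 6-month International data will be used. That might be read as limiting these subjects' 183-day contribution, but Table 5 sets no such condition.

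A reader might infer two stronger conclusions. One is that all 47 International subjects in the 100 are affected. They are not: once a 12-month visit is completed the subject has been assessed, and even at an early snapshot only those in certain day ranges are exposed. The other is that the rule would change the outcome of the 1-year performance-goal test. The documents do not show this. Table 5 defines an MDE-only rate, whereas the 1-year goal adds access and deployment failures. The SAP gives no cut-off for that analysis, and it follows subjects at least until the last one completes the 1-year visit. A count from an early snapshot therefore cannot be carried over to it.

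**Conclusion.** The concern holds as a flaw in the denominator rule. As written, unobserved time is scored as event-free in the 183- and 365-day MDE rates and in the other non-image rates through 1 year. Imaging rates are not affected, because Table 6 requires a readable image or a counted event.

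The bias is downward and its size cannot be fixed from the documents. Under the assumed 5 to 20 unseen subjects of 100, the 365-day rate would be understated by about 0.4 to 1.8 percentage points (7.4 − 7.0 to 8.8 − 7.0) relative to leaving those subjects out. At a mature cut-off the affected group is confined to subjects who missed the 12-month visit and have not exited. The reach to the 20% goal is conditional on Table 5 being used for that test. The stated 92% power is not in question. The rule should be changed before these rates are reported, but nothing here shows that a conclusion would be reversed.

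**What to change.** 1. Define duration in study for every subject, exited or not, as the day of last documented contact (visit, imaging, adverse event report or last-known-alive date) on or before the cut-off.
2. Compute the 183- and 365-day m/(m + k) rates only at a cut-off after every included subject's 12-month visit or the close of its window (Day 425). For US subjects at 183 days, the 6-month visit or its window close (Day 213, from 183 + 30) is enough. Events and non-events are then ascertained over the same period.
3. For any earlier snapshot, report Kaplan-Meier estimates censored at last contact. The SAP already uses this method beyond 1 year. The first change alone would not do at an immature snapshot: it keeps early events and drops event-free subjects between visits, which biases the rate upward.
4. State whether Table 5 governs the 1-year performance-goal analysis.

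The cost is SAP wording, slightly fewer evaluable subjects and later reporting of these rates. Last-known-alive dates are recorded at missed visits only where they are obtained (Protocol F.7.3), so some subjects will have no contact date between month 1 and month 12.
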